6.3. Handling of Dropouts or Missing Data

Intercurrent events (ICH E9R1) are events which occur after the treatment initiation and make it impossible to measure a variable or influence how it should be interpreted. Examples of such events include treatment discontinuation due to death or adverse events (AEs), rescue treatment, and loss to follow-up. The missing data methods described below handle intercurrent events in different ways.

6.3.1. *Non-Responder Imputation (NRI)*

The NRI method can be justified based on the composite strategy (ICH E9R1) for handling intercurrent events. In this strategy patients are defined as responders only if they meet the clinical requirements for response at the predefined time AND they remain on the assigned study treatment. Failing either criteria by definition makes them non-responders.

Analysis of binary efficacy and health outcome variables will be assessed using an NRI method. Patients will be considered as non-responder for the NRI analysis if they do not meet the clinical response criteria or have missing clinical response data at the analysis time point. Randomized patients with no postbaseline observations will also be defined as non-responders for the NRI analysis.

For the Maintenance Period, patient who relapse (see definition in [Table AMAK.6.5](#)) after re-randomization during the maintenance period will be considered to have entered the relapse period and will be non-responders for all subsequent visits of maintenance efficacy analysis.

For the Relapse Period, the response rates will be summarized by the weeks after relapse based on the number of patients with planned scheduled visit during the Relapse Period. Patients who complete the Week 52 treatment visit will, thereafter, not be counted in the numerator when calculating the response rate.

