Number of prior non-biologic systemic therapies ^e	No	0, 1, 2, >2		
Prior conventional systemic therapy ^f	No	Never used, Ever used	X	
Number of prior conventional systemic therapies ^f	No	0, 1, 2, >2		
Prior anti-TNF alpha ^g	No	Never used, Ever used	X	X
Prior anti-IL 17 ^g	No	Never used, Ever used	X	
Prior anti-TNF alpha ^g and/or Prior anti-IL 17 ^g	No	Anti-IL-17 only, Anti-TNF only, Both, Neither		
Prior topical therapy	No	Never used, Topical prescription therapy, Topical non-prescription therapy		
Prior phototherapy	No	Never used, Ever used	X	
Prior systemic therapy or phototherapy	No	Never used, Ever used	X	
Prior non-biologic systemic therapy or phototherapy	No	Never used, Ever used	X	
Prior biologic inadequate response (among those who had	No	Yes, No	X	

Variable	Quantitative Summary	Categorical Summary	Subgroup Analysis ^a	
			Induction	Maintenance
prior biologic therapy)				
Prior biologic loss of response (among those who had prior biologic therapy)	No	Yes, No	X	
Prior biologic intolerance (among those who had prior biologic therapy)	No	Yes, No	X	
Prior biologic inadequate response, loss of response, or intolerance (among those who had prior biologic therapy)	No	Yes, No	X	
Prior biologic failure ^h (among those who had prior biologic therapy)	No	Failed, Not failed	X	
Prior biologic failure ^h relative to prior biologic exposures	No	Not exposed, Exposed but not failed, Exposed and failed		
Prior systemic failure ^h (among those who had prior systemic therapy)	No	Failed, Not failed	X	
Prior failure, contraindication or intolerance to non-biologic systemic agents or phototherapy	No	Yes, No	X	X
Psoriasis Duration and Age at Onset				
Duration of psoriasis (years) ^l	Yes	<15, ≥15	X	
Duration of diagnosis (years) ^l	Yes	None		
Age at onset (years) ^k	Yes	<25, ≥25	X	
Area of Involvement				
Baseline facial involvement	No	Yes, No	X	
Baseline nail involvement	No	Yes, No	X	
Baseline scalp involvement	No	Yes, No	X	
Baseline palmoplantar involvement	No	Palm involvement only, Sole Involvement only, Both, Neither		
		Yes, No	X	
Baseline Psoriatic Arthritis	No	Yes, No	X	
Baseline Disease Severity				
Baseline PASI score	Yes	<20, ≥20	X	
		<15, ≥15	X	
Baseline sPGA score	Yes	Moderate (3), Severe (4), or Very severe (5)	X	
Baseline BSA (%)	Yes	<20%, ≥20%	X	
Baseline PSSI	Yes	None		
Baseline NAPSI	Yes	None		
Baseline PPASI	Yes	None		
Baseline PSS sign scores	Yes	0, ≥1		
Baseline PSS symptom score	Yes	0, ≥1		

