PASI	
Psoriasis Area and Severity Index (PASI): combines assessments of the extent of body-surface involvement in 4 anatomical regions (head and neck, trunk, arms, and legs) and the severity of scaling (S), redness (R), and plaque induration/infiltration (thickness, T) in each region, yielding an overall score of 0 for no psoriasis to 72 for the most severe disease (Fredriksson and Pettersson 1978). Severity is rated for each index (R, S, T) on a 0-4 scale (0 for no involvement up to 4 for very severe involvement):
 
 0 = none 1 = slight 2 = moderate 3 = severe 4 = very severe 
The body is divided into 4 anatomical regions comprising the head (h), upper limb (u), trunk (t), and lower limb (l). In each of these areas, the fraction of total body surface area affected is graded on a 0-6 scale (0 for no involvement; up to 6 for 90% - 100% involvement):
 
 0 = 0% (clear) 1 = >0% to <10% 2 = 10% to <30% 3 = 30% to <50% 4 = 50% to <70% 5 = 70% to <90% 6 = 90% to 100% 
The various body regions are weighted to reflect
	PASI score	
The composite PASI score is calculated by multiplying the sum of the individual-severity scores for each area by the weighted area-of-involvement score for that respective area, and then summing the 4 resulting quantities as follows:
 $PASI = 0.1(R_h + T_h + S_h)A_h + 0.2(R_u + T_u + S_u)A_u + 0.3(R_t + T_t + S_t)A_t + 0.4(R_l + T_l + S_l)A_l$ 
Where,
 
 R_h, R_u, R_t, R_l = redness score of plaques on the head, upper limb, trunk, and lower limb, scored 0-4 respectively; T_h, T_u, T_t, T_l = thickness score of plaques on the head, upper limb, trunk, and lower limb, scored 0-4 respectively; S_h, S_u, S_t, S_l = scaliness score of plaques on the head, upper limb, trunk, and lower limb, scored 0-4 respectively; A_h, A_u, A_t, A_l = numerical value translation of % area of psoriatic involvement score for the head, upper limb, trunk, and lower limb, respectively. 
PASI scores are treated as a continuous score, with 0.1 increments within these values.
	If any individual score is missing, the PASI score will not be calculated, hence, missing.
		PASI change from baseline	Calculated as: observed PASI – baseline PASI.	Missing if baseline or observed value is missing.

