		Time to first regaining PASI 90 or PASI 100 (i.e., 2 different analyses) after relapse	For patients who are observed to regain response during the Relapse Period, time will be from the start of the Relapse Period to the first measurement date where response was achieved.	Patients who are not observed to regain response will be censored after the date of their last visit during the Maintenance Period.
		Cumulative time with PASI 90 response after re-randomization through Week 52	Area under the curve (AUC) of PASI 90 response over time using trapezoidal rule (i.e. 100% when patients are PASI 90 responders at the visit and 0% when patients are non PASI 90 responders at the visit.) percentages of scheduled visits with PASI 90 response among all scheduled visits percentages of weeks with PASI 90 response	NRI if the observed value is missing.
		Relapse	The loss, at any visit, of $\geq 50\%$ of the Week 16 PASI improvement from baseline. That is, a patient will have relapsed during the Maintenance Period if their PASI score increases to greater than or equal to the midpoint between their baseline and Week 16 PASI score.	Missing if baseline, Week 16 or observed value is missing.
sPGA	Static Physician Global Assessment (sPGA): the physician's global assessment of the patient's psoriasis lesions at a given time point. Plaques are assessed for induration, erythema, and scaling, and an overall rating of psoriasis severity is given using the anchors of: clear (0), minimal (1), mild (2), moderate (3), severe (4), or very severe (5).	sPGA score	Range from 0 to 5: clear (0), minimal (1), mild (2), moderate (3), severe (4), or very severe (5).	Single item, missing if missing.
		sPGA (0,1) (Primary)	An sPGA assessed as either 0 or 1, which represents a clinically meaningful response of minimal plaque severity or complete resolution of plaque psoriasis.	Missing if sPGA is missing.
		sPGA (0)	An sPGA assessed as 0, which represents a clinically important endpoint indicating complete resolution of plaque psoriasis.	Missing if sPGA is missing.

Measure	Description	Variable	Derivation/Comment	Definition of Missing Components

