		PSS Symptoms Score	Calculated by summing the individual item scores as follows: itch NRS + pain NRS + stinging NRS + burning NRS.	If any of the 4 relevant item scores are missing, the score is missing.
		PSS Signs Score	Calculated by summing the individual item scores as follows: redness NRS + scaling NRS + cracking NRS.	If any of the 3 relevant item scores are missing, the score is missing.
		PSS Symptoms Score of 0	Free of itch, pain, stinging, and burning.	Missing if PSS Symptoms Score is missing.

Measure	Description	Variable	Derivation/Comment	Definition of Missing Components
	stinging, burning, redness, scaling, and cracking.	PSS Signs Score of 0	Free of redness, scaling and cracking.	Missing if PSS Signs Score is missing.
		PSS (Signs, Symptoms, items) Score change from baseline	Change from baseline = Observed PSS Score – Baseline PSS Score. Here “PSS Score” could refer to the Signs, Symptoms, or an item Score. Negative change indicates improvement and a positive change indicates deterioration of the condition.	Missing if either observed or baseline PSS score is missing.
PSSI	
Psoriasis Scalp Severity Index (PSSI): will be used if the patient has scalp psoriasis at baseline. The scalp will be assessed for erythema (redness), induration (hardness), and desquamation (shedding of skin) and percentage of area affected as follows:
 
Erythema, Induration, and Desquamation: 0 = Absent 1 = Slight 2 = Moderate 3 = Severe 4 = Severest Possible
 
Percent of Scalp Involved: 0 = none 1 = <10% 2 = 10 – 29% 3 = 30 – 49% 4 = 50 – 69% 5 = 70 – 89% 6 = 90 – 100%
	PSSI score	The PSSI score is a composite score derived from the sum of the scores for erythema, induration and desquamation multiplied by the score for the extent of scalp area involved (percent of scalp involved). The range is 0 to 72.	If any individual score is missing, the PSSI score will not be calculated, hence missing.
		PSSI score change from baseline	Calculated as: observed PSSI – baseline PSSI	Missing if baseline or observed value is missing
		PSSI score = 0	A PSSI response is defined as a PSSI score of 0, which is also referred to as scalp clearance.	Missing if PSSI score is missing

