PPASI	
Palmoplantar Psoriasis Area and Severity Index (PPASI): will be used if the patient has palmoplantar psoriasis at baseline. Both palms and soles on each hand and foot will be individually assessed for erythema, induration, desquamation and percentage of area affected as follows:
 
Erythema (E), Induration (I), and Desquamation (D):
 
 0 = None 1 = Slight 2 = Moderate 3 = Severe 4 = Very Severe 
Percent of Palm and Sole Area Covered:
 
 0 = None 1 = <10% 2 = 10 – 29% 3 = 30 – 49% 4 = 50 – 69% 5 = 70 – 89% 6 = 90 – 100% 	PPASI score	
The PPASI score is a composite score derived from the sum scores for erythema, induration, and desquamation multiplied by a score for the extent of palm and sole area involvement. The range is 0 to 72.
 $PPASI = 0.2(E_{rp} + I_{rp} + D_{rp})A_{rp} + 0.2(E_{lp} + I_{lp} + D_{lp})A_{lp} + 0.3(E_{rs} + I_{rs} + D_{rs})A_{rs} + 0.3(E_{ls} + I_{ls} + D_{ls})A_{ls}$ 
where:
 
$E_{rp}, E_{lp}, E_{rs}, E_{ls}$ = Erythema score of plaques on the right palm (rp), left palm (lp), right sole (rs), left sole (ls), scored 0-4 respectively;
 
$I_{rp}, I_{lp}, I_{rs}, I_{ls}$ = Induration score of plaques on the right palm (rp), left palm (lp), right sole (rs), left sole (ls), scored 0-4 respectively;
 
$D_{rp}, D_{lp}, D_{rs}, D_{ls}$ = Desquamation score of plaques on the right palm (rp), left palm (lp), right sole (rs), left sole (ls), scored 0-4 respectively;
 
$A_{rp}, A_{lp}, A_{rs}, A_{ls}$ = numerical value translation of % area covered for the right palm, left palm, right sole, and left sole, respectively.
	If any individual score is missing, the PPASI score will not be calculated, hence, missing.
		PPASI change from baseline	Calculated as: observed PPASI – baseline PPASI.	Missing if baseline or observed value is missing.
		PPASI percent improvement from baseline	
Calculated as:
 $Percent\ improvement\ from\ baseline = 100 \times \frac{Baseline\ PPASI - Observed\ PPASI}{Baseline\ PPASI}$ 
If a patient has experienced an improvement, this measure will be positive. If a patient has experienced a worsening in the condition, this measure will be negative.
	Missing if baseline or observed value is missing.

Measure	Description	Variable	Derivation/Comment	Definition of Missing Components
		PPASI 50	At least a 50% improvement in PPASI score from baseline.	Missing if baseline or observed value is missing.

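### A blank severity item makes PASI, PSSI or PPASI missing even in a clear region, where the formula already fixes that region's term at 0

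*SAP*

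**What the plan says.** SAP Section 6.10, Table AMAK.6.5, builds the PASI by "multiplying the sum of the individual-severity scores for each area by the weighted area-of-involvement score for that respective area" and adding the four results. Its missing-data rule is: "If any individual score is missing, the PASI score will not be calculated, hence, missing".

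The PSSI is one such product for the scalp, with the rule "If any individual score is missing, the PSSI score will not be calculated, hence missing". The PPASI adds four such products, for two palms and two soles, with the rule "If any individual score is missing, the PPASI score will not be calculated, hence, missing". None of the three rules makes an exception for an area score of 0.

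Under SAP Section 6.3.1, patients who "have missing clinical response data at the analysis time point" are non-responders. Table AMAK.6.6 applies the CMH test with NRI to PASI 75/90/100, PSSI = 0 and PPASI 50/75/100. PASI 90 at Week 16 is a primary endpoint. PASI 75 and PASI 100 and the Week 52 PASI 90 endpoint are under multiplicity control.

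Other instruments in Table AMAK.6.5 tolerate gaps. NAPSI averages the remaining fingernails if fewer than half are missing, the DLQI total allows one missing question, and each TSQM domain allows one missing item.

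**The concern.** The rule discards totals that need no imputation. With area score 0, a region's term is known and its blank severity items carry no information about the total.

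Section 6.3.1 justifies NRI by a composite strategy: a patient fails by not meeting the clinical criterion or by not remaining on assigned treatment. A patient whose recorded items prove a PASI 90 response, and who is still on treatment, fails on neither count, yet would be analysed as a failure.

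The case is sharpest for the PSSI, which has a single region. Scalp area 0 gives a total of 0, which is the response itself, but one blank severity item turns it into non-response.

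Patients with many clear regions are mostly responders, and responders are expected mostly on mirikizumab. At stake is the accuracy of the estimated response rates.

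**Working it through.** **1. Inputs.** The SAP Section 5.1 assumptions are:
- Induction: 400 mirikizumab and 100 placebo patients, Week 16 PASI 90 of 70% vs 3%, two-sided alpha 0.05.
- Maintenance: about 93 per group (400 × 0.70 / 3 = 93.3), Week 52 PASI 90 of 80% (250 mg), 70% (125 mg) and 10% (placebo), two-sided alpha 0.025.

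The formulas and missing-data rules come from Table AMAK.6.5. Neither document says how often items are blank, so every loss rate below is an assumption.

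**2. The plan's own figure.** Power = Φ[(|p1 − p0| − z × SE_pooled) / SE_unpooled]. It is about 100% for PASI 90 at Week 16 and about 100% for each maintenance comparison. The stated power above 95% is reproduced.

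**3. The formula at area 0.** A PASI region contributes w × (R + T + S) × A. With A = 0 this is 0 for all 125 combinations of R, T and S and for all four weights (0.1, 0.2, 0.3, 0.4).

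**4. A constructed patient.**
- Baseline, all severities 3, area scores 2, 2, 3, 3 (head, upper limb, trunk, lower limb): 0.1×9×2 + 0.2×9×2 + 0.3×9×3 + 0.4×9×3 = 1.8 + 3.6 + 8.1 + 10.8 = 24.3.
- Week 16: head area 0 with R, T and S blank; upper limb and trunk clear and fully recorded; lower limb R = 1, T = 1, S = 0, A = 1. PASI = 0.4 × 2 × 1 = 0.8, whatever the blanks would have been.
- Improvement: 100 × (24.3 − 0.8) / 24.3 = 96.7%, a PASI 90 response. Under the SAP rule the total is missing, and NRI gives non-response.

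**5. Effect on Week 16 PASI 90.** Let f be the share of true mirikizumab responders lost this way, with placebo held at 3%. The observed rate is 0.70 × (1 − f), and the number lost is 280 × f.

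| f (assumed) | Observed rate | Patients lost | Difference vs placebo |
|---|---|---|---|
| 0 | 70.0% | 0 | 67.0 points |
| 1% | 69.3% | 2.8 | 66.3 |
| 5% | 66.5% | 14 | 63.5 |
| 10% | 63.0% | 28 | 60.0 |
| 20% | 56.0% | 56 | 53.0 |

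If placebo responders are lost at the same rate, the difference is 0.67 × (1 − f), for example 53.6 points at f = 20%.

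**6. Effect on PASI 100.** Let r be the share of clear regions with a blank severity item. A PASI 100 patient has four clear regions. If blanks are independent across regions, the share lost is 1 − (1 − r)^4: 3.9% at r = 1%, 7.8% at 2%, 18.5% at 5%. If blanks cluster completely within patients, as a rater's habit would produce, the share lost is r itself: 1%, 2%, 5%.

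**7. Effect on power.** Even at f = 50%, with placebo unchanged, power is about 100% for induction PASI 90 (35% vs 3%), 99.6% for 250 mg (40% vs 10%) and 97.3% for 125 mg (35% vs 10%).

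**The case against.** The strongest reply is that the trigger may never occur. Each scale has a value for the clear case: 0 means none for PASI and PPASI, and absent for PSSI. A rater who follows the instrument enters 0 and nothing is lost. Protocol Appendix 3.2 also provides for computer edits of the case report form data. This stands: the documents do not show that blanks happen. They also do not describe mandatory entry or automatic zeros, so they do not show that blanks cannot happen.

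Second, Week 16 PASI 90 is partly covered. The tipping-point analysis (SAP Section 6.3.5) varies the response probability of missing patients from 0 to 1, and the categorical MMRM does not use NRI. This stands too, but neither changes the primary estimate, and neither is planned for PASI 75, PASI 100, the Week 52 endpoint, PSSI or PPASI.

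Third, requiring complete items is simple and conservative, and a rule that sets the term to 0 at area 0 could override recorded non-zero severities. The last part fails, because the existing formula already gives 0 there. Such contradictory entries should be queried in either case.

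A reader might infer two stronger claims that the documents do not support:
- **Palm-only and sole-only patients drop out of the PPASI at every visit.** Table AMAK.6.4 does list "Palm involvement only, Sole Involvement only, Both, Neither", but that shows only that such patients exist. Table AMAK.6.5 has each palm and sole assessed individually, so an uninvolved site should receive a 0.
- **A patient re-randomized as a responder becomes a Week 16 non-responder in the primary analysis, or has no defined relapse throughout maintenance.** The relapse rule does read "Missing if baseline, Week 16 or observed value is missing". But Protocol Section 5.1.3 needs a Week 16 PASI to classify patients and uses it again to identify relapse, so an incomplete score would probably surface at the visit. The documents do not describe a second, different derivation of the score.

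**Conclusion.** The point holds as a gap in the scoring rule. Read literally, Table AMAK.6.5 and Section 6.3.1 together can turn a fully determined response into a failure for PASI 75/90/100, PSSI = 0 and PPASI 50/75/100.

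Whether this happens depends on severity items being left blank in clear regions. The frequency is unknown and may be zero. If it does happen, the loss falls mostly on clear or nearly clear patients and understates mirikizumab response: by 0.7 points of the 70% PASI 90 rate for each 1% of responders affected.

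A reader might take this as a threat to the superiority conclusions. It is not one: any bias runs mostly against mirikizumab, power stays above 95% even under an extreme loss, and the other primary endpoint, sPGA (0,1), is a single item and unaffected. Only the accuracy of the estimates is in question.

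**What to change.** Replace the three missing-data rules in Table AMAK.6.5 with text such as:

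> When the recorded area score of a region is 0, or all three of its recorded severity scores are 0, the term for that region is 0 even if its other items are blank. The total is missing only if the term of at least one region cannot be determined from the recorded items. Contradictory entries are queried.

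For the PSSI the region is the scalp; for the PPASI it is each palm and each sole.

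The cost is the SAP wording, one programming rule and an edit check. No new data are needed and nothing is imputed, because the rule follows from the formula and is the same in every arm. If the case report form already forces zeros, no result changes. The rule should be in place before efficacy data are unblinded. A count by arm and visit of the totals it recovers would show whether the issue arose.

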		PASI percent improvement from baseline	
Calculated as:
 $100 \times \frac{\text{Baseline PASI} - \text{Observed PASI}}{\text{Baseline PASI}}$	Missing if baseline or observed value is missing.

Measure	Description	Variable	Derivation/Comment	Definition of Missing Components
	their respective proportion of body surface area.		If a patient has experienced an improvement, this measure will be positive. If a patient has experienced a worsening in the condition, this measure will be negative.	
		PASI 75	A clinically meaningful response; at least a 75% improvement in PASI score from baseline.	Missing if baseline or observed value is missing.
		PASI 90 (Primary)	Higher level of clearance; at least a 90% improvement in PASI score from baseline.	Missing if baseline or observed value is missing.
		PASI 100	Complete resolution of plaque psoriasis; a 100% improvement in PASI score from baseline.	Missing if baseline or observed value is missing.
		Stability of PASI 90 / PASI 100 from Week 16 to each visit up to Week 52	Patient has PASI 90 / PASI 100 for all non-missing visits starting from Week 16 to (and including all between scheduled visits if any) each visit up to Week 52.	Missing if PASI 90 / PASI 100 is missing any of Week 16 to each visit up to Week 52. Also missing when patient has relapsed/ discontinued study treatment at or before the analysis visit.
		Time to first achieving PASI 100, PASI 90 or PASI 75 (i.e., 3 different analyses) during Induction Period	For patients who are observed to meet the response criteria during the Induction Period, time will be from the start of the Induction Period to the first measurement date where the patient met the response criteria.	Patients not observed to meet response criteria during the Induction Period will be censored after the date of their last measurement during the Induction Period.
		Time to first loss of PASI 90 or relapse (i.e., 2 different analyses) after re-	For patients who are observed to relapse/lose response during the Maintenance Period, time will be from the start of the Maintenance Period to the first measurement date where the patient relapsed.	Patients who are not observed to relapse/lose response during the Maintenance Period will be censored after the date

Measure	Description	Variable	Derivation/Comment	Definition of Missing Components
		randomization		of their last visit during the Maintenance Period.

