	Time to first achieving PASI 100, PASI 90, or PASI 75 (i.e., 3 different analyses)	KM analysis (censoring described in Table AMAK.6.5)	Induction ITT;	All visits in corresponding periods
	Time to first loss of PASI 90	KM analysis (censoring described in Table AMAK.6.5)	Re-randomized Maintenance ITT	All visits in corresponding periods
	Time to first loss of PASI 100	KM analysis (censoring described in Table AMAK.6.5)	Re-randomized Maintenance ITT in patients achieved PASI 100 at Week 16	All visits in corresponding periods
	Stability of PASI 90 up to Week 52	CMH analysis with NRI	Re-randomized Maintenance ITT	All visits in corresponding periods
	Stability of PASI 100 up to Week 52	CMH analysis with NRI	Re-randomized Maintenance ITT in patients achieved PASI 100 at Week 16	All visits in corresponding periods
PASI ≤5; PASI ≤3; PASI ≤2; PASI ≤1	CMH analysis with NRI	Induction ITT; Re-randomized Maintenance ITT;	All visits in corresponding periods	

Measure	Variable	Analysis Method (Section 6.1.4)	Population (Section 6.1.1)	Time Point				
	PASI change from baseline	MMRM; ANCOVA with mBOCF	Induction ITT; Re-randomized Maintenance ITT;	All visits in corresponding periods				
		Summary statistics (As observed)	Non-re-randomized Maintenance; Re-randomized Relapsed	All visits in corresponding periods				
	Percent improvement from baseline	MMRM; ANCOVA with mBOCF	Induction ITT; Re-randomized Maintenance ITT	All visits in corresponding periods				
		Summary statistics (As observed)	Non-re-randomized Maintenance; Re-randomized Relapsed	All visits in corresponding periods				
	Cumulative time with PASI 90 response after re-randomization through Week 52	ANCOVA for AUC of PASI 90 response over time; ANCOVA for percentages of scheduled visits with PASI 90 response among all scheduled visits ANCOVA for percentages of weeks with PASI 90 response in maintenance period	Re-randomized Maintenance ITT	All visits in corresponding periods through Week 52				
					Cumulative time with PASI 100 response after re-randomization through Week 52	ANCOVA for AUC of PASI 100 response over time ANCOVA for percentages of scheduled visits with PASI 100 response among all scheduled visits ANCOVA for percentages of weeks with PASI 100 response in maintenance period	Re-randomized Maintenance ITT in patients achieved PASI 100 at Week 16	All visits in corresponding periods through Week 52

Measure	Variable	Analysis Method (Section 6.1.4)	Population (Section 6.1.1)	Time Point

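### SAP Table AMAK.6.5 uses the relapse date as the only event date in a row that also defines time to first loss of PASI 90, so that second analysis is misdated as written

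*SAP*

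**What the plan says.** SAP Table AMAK.6.5 (Section 6.10) has one PASI row for time to first loss of PASI 90 and time to relapse, and states that these are two different analyses. The row has three working parts:

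- **Event condition:** "For patients who are observed to relapse/lose response during the Maintenance Period".
- **Event date:** counted from the start of the Maintenance Period "to the first measurement date where the patient relapsed".
- **Censoring:** "Patients who are not observed to relapse/lose response during the Maintenance Period will be censored after the date" of their last visit in that period.

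The event condition and the censoring rule cover both events. The event date names relapse only.

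Both terms are defined in the same table. PASI 90 is described as "Higher level of clearance; at least a 90% improvement in PASI score from baseline". A patient relapses "if their PASI score increases to greater than or equal to the midpoint between their baseline and Week 16 PASI score"; Protocol Section 5.1.3 defines relapse in the same way.

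SAP Table AMAK.6.6 lists "Time to first loss of PASI 90" and time to relapse as separate Kaplan-Meier analyses in the Re-randomized Maintenance ITT population. For each it refers back to Table AMAK.6.5 for censoring, and it gives no event date of its own. SAP Section 6.1.4 attaches a hazard ratio and a stratified log-rank test to the time-to-event analyses.

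**The concern.** Relapse is a defined term, so it cannot simply be read as loss of response. It is also a much more severe event than loss of PASI 90. No other part of the SAP supplies a date for first loss of PASI 90, so a programmer who follows the row as written would apply the wrong date to one of its two analyses.

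Neighbouring rows avoid this. Time to first achieving PASI 75, 90 or 100 ends when the relevant response criterion is met. Time to regaining PASI 90 or 100 ends when response is achieved. Those wordings work for every analysis in their rows; this one works for only one of two.

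At stake is a supportive durability analysis. Two programmers working from this text could produce different curves, hazard ratios and p-values for loss of PASI 90.

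**Working it through.** **Inputs**

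- B = baseline PASI; at least 12 at entry (Protocol Section 6.1, criterion 1A).
- W = Week 16 PASI. Only mirikizumab patients with PASI 90 at Week 16 are re-randomized (SAP Section 5), so W lies between 0 and 0.10 x B.
- Definitions of PASI 90 and relapse: SAP Table AMAK.6.5.
- About 93 patients per maintenance arm, with assumed Week 52 PASI 90 maintenance of 80% (250 mg), 70% (125 mg) and 10% (placebo): SAP Section 5.1.

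**Step 1: the plan's two wordings of relapse agree.** Losing half of the Week 16 improvement means PASI reaches W + 0.5 x (B - W) = (B + W)/2, which is the midpoint that the SAP states.

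**Step 2: the two thresholds.**

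- Loss of PASI 90: PASI > 0.10 x B.
- Relapse: PASI >= (B + W)/2. With W from 0 to 0.10 x B, this is 0.50 x B to 0.55 x B, or 5.0 to 5.5 times the loss-of-PASI 90 threshold. In terms of improvement, it must have fallen to 50% (W = 0) or to 45% (W = 0.10 x B).

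| Baseline | Week 16 PASI | PASI 90 lost when PASI is | Relapse when PASI is |
|---|---|---|---|
| 12 | 0 to 1.2 | above 1.2 | at least 6.0 to 6.6 |
| 20 | 0 to 2.0 | above 2.0 | at least 10.0 to 11.0 |
| 20 | 1.0 | above 2.0 | at least (20 + 1)/2 = 10.5 |

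Every relapse is therefore also a loss of PASI 90, at the same visit or an earlier one. The reverse does not hold.

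**Step 3: apply the row literally to the loss-of-PASI 90 analysis.**

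| Patient | Event condition met? | Censored? | Date given by the row |
|---|---|---|---|
| Loses PASI 90 and relapses at the same visit | yes | no | correct |
| Loses PASI 90, relapses at a later visit | yes | no | too late |
| Loses PASI 90, never relapses | yes | no | none |
| Keeps PASI 90 throughout | no | yes | last visit in the period |

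**Step 4: how late.** This depends on the course of PASI, which the documents do not give. As an illustration only, assume a linear fall in percent improvement from Week 16, assessed every 4 weeks, starting from 90% to 100% improvement:

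| Fall per 4 weeks | First loss of PASI 90 | Relapse |
|---|---|---|
| 30 points | Week 20 | Week 24 |
| 20 points | Week 20 | Week 28 |
| 10 points | Week 20 to 24 | Week 36 |
| 3 points | Week 20 to 32 | not reached by Week 52 |

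**Step 5: how many.** Patients planned not to maintain PASI 90 at Week 52 number 93 x 0.20 = 18.6 (250 mg), 93 x 0.30 = 27.9 (125 mg) and 93 x 0.90 = 83.7 (placebo). These are not counts of first losses. The Week 52 analysis uses non-responder imputation (SAP Section 6.3.1), so non-response there can include dropouts, and it leaves out patients who lost and then regained PASI 90. The share who would never relapse is not stated either. The numbers dated late or left undated therefore cannot be derived.

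**The case against.** The strongest reply is that this is one dropped phrase. The row's title, event condition and censoring rule all cover both events, PASI 90 is defined nearby, and Table AMAK.6.6 keeps the two analyses apart. Read as a whole, each analysis was surely meant to end at its own event. That is probably the intent. It does not supply the missing date, however, and the clause that sets the date uses a defined term with a different meaning.

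The reply is also right that the analysis carries limited weight. Time to first loss of PASI 90 is not a protocol-defined endpoint and is outside multiplicity control. SAP Section 6.1 says only that such additional results may appear in the study report. PASI 90 by visit, stability of PASI 90 and cumulative time with PASI 90 describe durability separately.

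A reader might go further and infer any of the following; the documents support none of them.

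- **The loss curves would largely duplicate the relapse curves and overstate durability.** That would require patients who lose PASI 90 without relapsing to be censored or dropped. The censoring rule excludes them, so they are left undated, and the result depends on how the programmer resolves that.
- **The active arms would be affected most.** Late dating can also reach placebo patients, who make up most of the planned Week 52 non-maintainers. The net effect on the hazard ratio is not determined.
- **About half of the active-arm events would have no date.** That figure only returns an assumption that half of those patients never relapse.

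**Conclusion.** The event date is wrong as written for one of the two analyses that the row governs. The gap between thresholds (above 0.10 x baseline against 0.50 to 0.55 x baseline) follows from the SAP's own definitions and needs no assumption. The consequence is late dates for patients who relapse at a visit after losing PASI 90, and no date for those who lose PASI 90 without relapsing. The length of the delay in the illustration rests on an assumed linear course.

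This is a minor point. Time to relapse carries the correct event date, and the major secondary endpoint of PASI 90 maintenance at Week 52 (Cochran-Mantel-Haenszel test with non-responder imputation) does not use this rule.

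There is a separate small gap. Table AMAK.6.6 also sends time to first loss of PASI 100 and time to first loss of sPGA (0,1) to Table AMAK.6.5 for censoring, but that table has no row for either. This is missing text and is not evidence that those analyses would be dated by relapse.

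**What to change.** Split the row in Table AMAK.6.5.

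- **Loss of PASI 90:** from the start of the Maintenance Period to the first assessment after re-randomization with less than 90% improvement in PASI from baseline.
- **Relapse:** from the same start to the first assessment meeting the relapse criterion.

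Let each censoring cell name its own event. In the same edit, add rows for loss of PASI 100 and loss of sPGA (0,1), each dated to the first assessment at which that response is no longer met, with censoring stated.

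The cost is SAP table wording. It needs no new data, visits or analyses, and is best made before the Week 52 database lock.
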